## **5.2 Immunosuppression Dosage and Administration**

Participants will continue their prescribed regimen of oral tacrolimus and mycophenolate. No changes will be made to the subject’s medication therapy as part of the study. The participant will continue their own supply of medication provided by their local pharmacy. Medication will not be supplied by the study. Dose adjustments may be made by the treating provider based on standard of care laboratory results or as determined by the treating provider to be clinically indicated. Dose adjustments will be documented in the study record.

The investigator will promote compliance by instructing the subject to take the study drug exactly as prescribed and by stating that compliance is necessary for the subject’s safety and the validity of the study. The subject should be instructed to contact the investigator if he/she is unable for any reason to take the study drug as prescribed. If vomiting occurs within 2 hours after administration of the dose on a sample collection day, the patient may be asked to repeat the collection at a later date at the discretion of the investigator. Adherence to the immunosuppressive regimen will be monitored using patient self-report and patient diary review.

## **5.3 Concomitant Medications/Treatments**

Concomitant medications will be administered per institution standard of care. Concomitant medication is defined as any prescription or over-the-counter preparation including vitamins and supplements. Concomitant medications will be recorded at the time of consent and visit 2 during part 2 of the study.

## **5.4 Duration of Study Involvement**

Part 1: Study participant may continue for up to 7 days or until one of the following criteria apply:

- Subject's immunosuppressive regimen no longer includes tacrolimus and mycophenolate
- Subject voluntarily withdraws
- Study completes the study assessments (2 paired sample collections)
- Subject is discharged
- Subject hemoglobin falls below 8g/dL

Part 2: The intervention may continue for 26 weeks or until one of the following criteria apply:

- Subject's immunosuppressive regimen no longer includes tacrolimus and mycophenolate.
- Subject voluntarily withdraws from treatment
- Subject transfers care from the Michigan Medicine
- Subject completes the required study assessments OR
- General or specific changes in the subject's condition render the subject unacceptable for further treatment in the judgment of the investigator

### **5.5 Off Intervention Criteria**

Subjects will be removed from the protocol intervention when any of the criteria listed in Section 5.4 apply. Document in the source the reason for ending the protocol and the date the subject was removed from the protocol. All subjects who discontinue treatment should comply with protocol specific follow-up procedures as outlined in Section 5.7. The only exception to this requirement is when a subject withdraws consent for all study procedures or loses the ability to consent freely.

### **5.6 Duration of Follow-Up**

Due to the minimal risk and nature of the intervention participants will not be followed beyond the completion of study visits.

### **5.7 Off Study Criteria**

Subjects may request to withdraw from the study at any time, or they may be withdrawn at the discretion of the investigator for safety, behavioral, or administrative reasons. Prior to study withdrawal, participants may be asked if they are willing to complete the end of study survey and be considered for participation in the qualitative interview regarding their experience.

The reason(s) for discontinuation from study will be documented and may include:

1. Subject withdraws consent (termination of treatment and follow-up);
2. Loss of ability to freely provide consent through imprisonment or involuntary incarceration for treatment;
3. Subject is unable to comply with protocol requirements;
4. Treating physician judges that continuation on the study would not be in the subject's best interest;

5. Lost to Follow-up. If a research subject cannot be located for 3 months, the subject may be considered “lost to follow-up.” All attempts to contact the subject during the three months must be documented;
6. Termination of the study by The University of Michigan
7. Subject completes protocol treatment and follow-up criteria.

### **5.8 Subject Replacement**

Part 1: Enrolled subjects may be replaced if paired samples are not successfully obtained on at least one occasion.

Part 2: Enrolled subjects may be replaced if they do not attempt at least one at-home blood collection.

## **6.0 STUDY PROCEDURES AND EFFICACY ASSESSMENT**

### **6.1 Study Procedures and Assessments**

This section contains a list and description of the study evaluations.

Part 1:

- During study visits 1 and 2 the following specimens will be collected for study purposes:
  - One 6-mL red top tube
    - One will be sent to the Michigan Medicine clinical laboratory for determination of mycophenolic acid and mycophenolic acid glucuronide concentration from serum. The results will be reported in the electronic medical record and will be available to the patient's clinical care team.
  - Four 20- $\mu$ L capillary dried blood samples via Tasso-M20 device for determination of tacrolimus, mycophenolic acid, mycophenolic acid glucuronide, and ganciclovir (if applicable) concentrations by the University of Michigan PK Core. These results will be considered investigational and will not be shared with the patient or care team.
  - Two 20- $\mu$ L capillary dried blood samples via Mitra device for determination of tacrolimus, mycophenolic acid, mycophenolic acid glucuronide, and ganciclovir (if applicable) concentrations by the University of Michigan PK Core. These results will be considered investigational and will not be shared with the patient or care team.

Standard of care labs will also be drawn at this time and processed by the Michigan Medicine clinical laboratory. Results for hemoglobin, hematocrit, albumin, and tacrolimus concentration will be collected from the electronic medication record for study purposes.

Study staff will collect any remaining/leftover blood from the Michigan Medicine clinical laboratory for additional analysis in the University of Michigan PK Core.

Participants will also complete self-report questionnaires describing and comparing the sample collection methods (Appendix B)

**Part 2:**

- Demographics including height and weight: will be recorded as reported by the patient or documented in the electronic medical record during the screening visit.
- Education on Tasso device utilization and diary documentation will occur after consent has been obtained at the baseline visit (may be the same day as consent). Education will be provided in a private space (such as clinic room) if completed in person. Education may also be conducted virtually at time where the patient can secure privacy.
- Biological specimen collection and laboratory evaluations:
  - During home-collection 1 and 2 the following specimens will be collected for study purposes:
    - Four 20- $\mu$ L capillary dried blood samples via Tasso-M20 device will be obtained at 4 time points (0, 1, 4, and 8hrs after morning tacrolimus/mycophenolate administration). A total of 320  $\mu$ L will be collected during each home-collection. These samples will be used for determination of tacrolimus, mycophenolic acid, mycophenolic acid glucuronide concentrations by the University of Michigan PK Core. These results will be considered investigational and will not be shared with the patient or care team.
    - The Tasso-M20 device will be provided to the patient prior to each sample collection via US mail. The patient will also be provided with a pre-paid mailer to return the samples to the study site.
    - Each collection day will require four Tasso devices (one for each time point). The devices will be numbered to facilitate patient use.

The results of any study-specific laboratory evaluations completed by the PK core will not be used to adjust medication therapy or be provided to the participant. The mycophenolate trough concentrations in addition to the standard of care labs processed by the Michigan Medicine Clinical lab will be available in the electronic health record for review by the participant.

- Administration of study instruments for subject-reported outcomes (Appendix C):
  - During the Baseline visit participants will complete questionnaire packet 1 which includes:
    - PROMIS Self-efficacy: Managing Medications/Treatments (8 items)
    - Medical Outcomes Social Support Scale (19 items)
    - Transplant Effects Questionnaire (worry, guilt, disclosure, and responsibility) (18 items)
    - Kidney Transplant Understanding Tool (abbreviated to the 20 items related to medication therapy and monitoring)
  - During the home collections 1 and 2 participants will complete the study diary which includes:
    - Medication dose times for the 48 hr prior to collection

- Sample collection times
- During the home collections 1 and 2 participants will complete ecological momentary assessments via text message
  - Pain intensity
  - Interruption in daily routine
  - Difficulty of sample collection
  - 48 hours after sample collection safety will be assessed via text message
- At end of study participants will complete questionnaire packet 2 which includes:
  - Self-reported adherence assessment
  - Acceptability and Feasibility of Implementation Measure (8 items)
- During visit 3 selected participants will participate in a semi-structured qualitative interview. The interview guide is provided in Appendix D.

## 6.2 Safety/Tolerability

Patients will complete ecological momentary assessments to document the participants experience by rating pain intensity, interruption in daily routine, and difficulty on a scale of 0 to 10 at the time of each Tasso sample collection. Forty-eight hours after sample collection participants will be asked if they experienced any adverse events including bruising, bleeding, and/or signs of infection. Analyses will be performed for all subjects who provided at least one blood sample.

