### 7.1 Adverse Event Reporting Requirements

Since the responsibility of the management of the patient's transplant regimen is retained by the health care providers at the University of Michigan Transplant Center and not dictated by the study protocol, deaths and hospitalizations will typically not be study related. Serious adverse events (SAEs) and adverse events (AEs) that are related to the participant's kidney transplant or other chronic disease conditions are not unanticipated and therefore will not be considered reportable to the IRB. For the sake of our study purposes and outcomes we will track SAEs and AEs related to study participation.

Adverse event data will be reviewed by the project leadership team and will be summarized in reports quarterly. Non-serious (mild/moderate) adverse event data will be reported to the IRB in annual renewals. SAEs related to study participation will be reported to the IRB within 7 calendar days of identification by the study team. A privacy violation or breach of confidentiality will be reported to the IRB within 7 calendar days and to the Corporate Compliance office within 24 hours of identification.

Definition of Adverse Events (AEs): AEs that are of particular interest to our study and that we will specifically track include problems associated with capillary sampling (infection, bruising, and bleeding at the site of lancet puncture) and text message communication (privacy breach). Capillary sampling AEs will be assessed at 48 hours after collection via text message requesting patients to self-report (Table 1). We will also assess for hospitalizations, urgent care/emergency room visits, and death. These events will be collected via electronic record review or self-report.

The severity or grade of an adverse event may be measured using the following definitions:

Mild: Noticeable to the subject, but does not interfere with subject's expected daily activities, usually does not require additional therapy or intervention, dose reduction, or discontinuation of the study.

Moderate: Interferes with the subject's expected daily activities, may require some additional therapy or intervention but does not require discontinuation of the study.

Severe: Extremely limits the subject's daily activities and may require discontinuation of study therapy, and/or additional treatment or intervention to resolve.

The investigator or co-investigator is responsible for assignment of attribution.

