## 8.0 DEVICE INFORMATION

The Tasso OnDemand is a sterile, disposable, integrated capillary blood collection device, including a lancet assembly and a detachable reservoir for the collection of blood.

The Tasso-M20 is used for the self-collection and storage of capillary blood from minimally trained users and shipping to a central laboratory for analysis. This configuration is available commercially and is registered with the FDA as a class 1 blood collection and container system. Tasso, Inc has validated the device utilizing the safety, sterility, packaging, and biocompatibility test methods required by the FDA for a medical device that interfaces with the body for less than 24 hours.

The mechanism is very simple to operate and enables the collection of a blood sample at the press of button. The device is placed on the skin of the upper arm and remains in position using an adhesive backing. The device is actuated by pressing the central button, causing an internal spring to contract and a plunger, containing a single 16-gauge stainless-steel lancet which penetrates 2.5mm into the skin. Upon actuation of the device, the lancet penetrates the skin, is immediately retracted (does not remain deployed for the whole wear time), and locks in an inactive position to prevent re-use. The lancet puncture causes blood to pool on the surface of the skin, which is further enhanced by the small amount of vacuum (~40 kPa). The base of the device is designed to collect the blood pooling on the surface of the skin and channel the blood into a detachable reservoir. The blood collection is stopped after the blood reaches an indicator on the reservoir (fill window for the dried blood configuration for a total sample of 80 $\mu$ L).

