### **9.5 Sample Size and Accrual**

Part 1: The expected LC-MS/MS assay coefficient of variation (CV) of >5% with a range ratio of >25 requires 40 participants with 80 paired dried and venous samples (2 pairs from each participant) to clinically validate the assay, including validation of the anticipated

mycophenolate conversion factor. To account for participants unwilling to provide additional samples, up to 90 participants may be enrolled.

Part 2: Compared to the previous rate for successful sample collection of 55% reported in the literature, the selected sample size of 45 participants will provide this pilot study >90% power to detect a 25% difference in successful sample collection (anticipated overall success of 80% in both groups).

The sample size is also adequate to assess the secondary and exploratory outcomes. Additionally, the 45 participants will provide 80% power for a 95% confidence interval to identify a 10-point difference in the absolute prediction error (APE) between AUC calculated from all 4 samples and estimates using different sampling combinations for tacrolimus. Finally, the convenience sample of the included patients will be used for the quantitative analysis to provide preliminary data describing the relationships between Theoretical Domain constructs and successful competition of home-based TDM. Qualitative interviews will be conducted with a minimum of 10 participants or until data saturation is reached.

Subjects will be considered evaluable if they complete the baseline survey and attempt to complete at least 1 home AUC collection.

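### The section 6.2 safety and tolerability analysis requires a blood sample, so a participant who activated a device but provided no sample counts as evaluable yet falls outside it

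*Combined protocol and SAP*

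**What the plan says.** Section 6.2 describes two kinds of data. Tolerability is measured by participants "rating pain intensity, interruption in daily routine, and difficulty on a scale of 0 to 10 at the time of each Tasso sample collection". Safety is measured by a later question: "Forty-eight hours after sample collection participants will be asked if they experienced any adverse events including bruising, bleeding, and/or signs of infection". The section then fixes the analysis set: "Analyses will be performed for all subjects who provided at least one blood sample". Section 6.1 lists these text-message assessments under Part 2 only.

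Other sections bear on who should be counted:

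- Section 8.0, on the device: "Upon actuation of the device, the lancet penetrates the skin, is immediately retracted".
- Section 9.5, on evaluability: "Subjects will be considered evaluable if they complete the baseline survey and attempt to complete at least 1 home AUC collection".
- Section 5.8, on replacement in Part 2: "Enrolled subjects may be replaced if they do not attempt at least one at-home blood collection".
- Section 7.1, on adverse events: "For the sake of our study purposes and outcomes we will track SAEs and AEs related to study participation". The events of particular interest there include infection, bruising and bleeding where the lancet entered.

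No section adds a separate analysis of participants who tried and obtained nothing.

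**The concern.** A safety set is normally defined by exposure. Here the exposure is the puncture, and obtaining blood is something that happens, or fails to happen, afterwards. Requiring a sample therefore selects participants on a post-exposure result. It also makes the safety set narrower, on this criterion, than the evaluable set in section 9.5, which needs only an attempt.

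What is at stake is the description of how easy and tolerable home collection is. Someone who could not obtain any sample is a natural high scorer on difficulty, and leaving that person out makes the device look easier to use than it was for those who tried it. The word 'provided' is also undefined. If it means received at the study site, participants who collected samples but never mailed them are left out too.

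**Working it through.** The plan states no size or event rate for the safety set, so there is no figure to reproduce. The check compares definitions and then bounds the effect under stated assumptions.

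**Step 1. Definitions side by side.** Take a Part 2 participant who completed the baseline survey, activated one or more devices, and provided no sample.

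| Section | Criterion | Status of this participant |
|---|---|---|
| 8.0 | Puncture occurs at actuation | Exposed |
| 9.5 | Survey plus an attempt | Evaluable |
| 5.8 | Replaceable only if no attempt | Not replaceable under this rule |
| 7.1 | Related events tracked, no sample needed | Events tracked |
| 6.2 | At least one sample provided | Excluded |

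Only section 6.2 excludes this participant.

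**Step 2. How many could be excluded.** Section 6.1 gives four devices per collection day and two collection days, so 4 × 2 = 8 planned devices per participant. The sample size is 45 (section 9.5).

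- Loose upper limit. Everyone with no sample is also unsuccessful on the primary endpoint. At the anticipated 80% success, 45 × 0.20 = 9. At the 55% literature rate, 45 × 0.45 = 20.25, about 20. These counts also contain late, partial and non-attempting participants, so the excluded group is smaller.
- Assumed per-device failure rate q, with each participant giving up after a first failed device: 45q = 2.25 at q = 5%, 4.5 at 10% and 9 at 20%.
- Same q, with all eight devices tried and failures independent: 45q⁸ = 45 × 0.2⁸ ≈ 0.0001 at q = 20%, and less at lower q.

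The excluded group therefore consists mainly of people who stop early or whose failures are correlated. The documents give no rate for either.

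**Step 3. Effect on difficulty.** Assume a mean rating of 8 among k excluded participants and 3 among the rest. The mean over all 45 is ((45 − k) × 3 + k × 8)/45.

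- k = 1: (132 + 8)/45 = 3.11.
- k = 4: (123 + 32)/45 = 3.44.

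Section 6.2 as written would report 3.0 in both cases.

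**Step 4. Effect on an event proportion.** Let the rate be 20% among sample providers and r among k excluded participants, both assumed. The rate over all 45 is ((45 − k) × 0.20 + k × r)/45.

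| k | r = 50% | r = 0% |
|---|---|---|
| 1 | 9.3/45 = 20.7% | 8.8/45 = 19.6% |
| 3 | 9.9/45 = 22.0% | 8.4/45 = 18.7% |
| 9 | 11.7/45 = 26.0% | 7.2/45 = 16.0% |

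The rule reports 20% throughout. The sign of the error depends on r, about which the documents say nothing.

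**The case against.** The strongest reply is that the rule is lenient. It does not require success on the primary endpoint, which needs all four collections documented in their window and a postmark within 48 hours of planned collection. One sample, even late or partial, keeps a participant in the analysis, and ratings from that participant's failed devices are not excluded. Section 11.b has staff telephone participants whose samples have not arrived, which should enlarge the set further. Safety and tolerability in Part 2 is not a listed objective, and section 10 treats the study as minimal risk. All of this stands, and it limits the size of the problem. It does not remove the mismatch between sections 6.2 and 9.5.

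Three stronger readings are tempting, and the documents do not support them.

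- A reader might infer that as many as 9 of 45 would be dropped. That number counts every kind of primary-endpoint failure and is only a loose cap at 80% success.
- A reader might infer that bruising and bleeding rates are biased downward. No data in the documents show this, and a puncture that yields no blood may bleed less. An illustration such as 0/43 reported in place of 2/45 needs every event in the cohort to fall on participants without a sample.
- A reader might infer that adverse events in these participants are lost. Section 7.1 tracks related events without requiring a sample and provides for quarterly summaries and reporting to the IRB, and section 10 has staff review the message logs for complications.

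It is also an inference, not a stated fact, that the ratings and the 48-hour answers will exist for failed attempts. Section 5.1 ties the messaging timeline to anticipated collection dates and times, which favours the inference. Section 6.2, however, words both assessments relative to sample collection.

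**Conclusion.** The point holds as a definitional mismatch with a probably small effect. Section 6.2 conditions on a result that follows the exposure, and sections 9.5 and 5.8 use the attempt. Participants who activated a device and provided no sample at all fall between the two.

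The number affected is likely to be few of 45, but it cannot be computed from the documents. Under the assumed ratings above, one such participant moves mean difficulty by about 0.1 point and four move it by about 0.4. Understatement of difficulty is the most plausible consequence. The direction for pain, bruising and bleeding is uncertain. The effect is confined to the section 6.2 summary and touches neither the primary endpoint nor event tracking under section 7.1. It would be wider if 'provided' means received at the site.

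**What to change.** Replace the last sentence of section 6.2 with: 'Safety and tolerability will be analysed in all participants who activated at least one collection device, whether or not a sample was obtained or returned.' Add a sentence stating that the 0 to 10 ratings and the 48-hour question also apply to failed attempts. This settles the meaning of 'provided' and brings section 6.2 into line with the attempt-based definitions in sections 9.5 and 5.8.

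As an optional detail, the section could say that a non-reply to the 48-hour text is treated as missing and that reply rates are given by arm. Nothing in the plan says non-replies would be counted as event-free, so this is clarification only.

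The cost is two sentences, with no new instrument, visit or change in sample size. Reported tolerability may be slightly less favourable.
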